Exploratory Endpoints	
Immunogenicity Endpoint:
 
 • ADAs against BT200 
Pharmacodynamic Endpoints:

1.5.1

	
 • Platelet Function Analyzer (PFA-100®) • VWF:ristocetin co-factor assay (VWF:RiCo) • Multiplate electrode platelet aggregometer (ristocetin) • Enzyme-linked immunosorbent assay (ELISA) for unbound VWF-A1 domain (REAADS®) 
Biomarker Endpoints:
 
 • VWF antigen and propeptide • Factor VIIIc activity • aPTT FS (elagic acid) • Thrombin generation Calibrated Automated Thrombogram (CAT) assay (Thrombinoscope®)
Statistical Considerations	
Sample Size Calculation:
 
As this study is exploratory and descriptive in nature, no inferential statistical testing is planned and therefore an exact sample size requirement cannot be specified. The number of NHVs planned to be included is expected to be sufficient to fulfill the study's objectives, but not excessive.
 
Analysis Plan:
 
For the analysis of AEs, summary tables will be generated for the incidence of AEs overall and by severity. The same will be calculated for serious adverse events (SAEs), related AEs, and related SAEs. The AE and SAE summary tables will provide the number and percentage of subjects with AEs and the 95% confidence intervals for the event rates. All safety analyses will be performed within the Safety Population.
 
Pharmacokinetic sampling results (serum concentration of BT200) will be tabulated descriptively by sampling time point. The area under the curve from 0 to 24 hours ($AUC_{[0-24]}$) and area under the curve from time 0 to time t ($AUC_{[0-t]}$) will be calculated via trapezoidal rule and will be tabulated together with the maximum plasma concentration (C_{max}) and time to maximum plasma concentration (T_{max}), descriptively.
 
Details regarding further safety endpoints and the analysis of secondary or exploratory endpoints will be described in the Statistical Analysis Plan.

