1.3 Endpoints

1.3.1 Primary Endpoint

Overall safety and tolerability of BT200, assessed in terms of:

- Serious, drug-related adverse events (AEs)
- Premature terminations due to drug-related AEs
- Patterns of serious or non-serious, drug-related AEs, and/or clinically relevant laboratory abnormalities, vital signs, ECGs, or physical findings suggestive of one or more specific target organs for toxicity of BT200
- Clinically evident bleeding

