2.12 Analysis Populations

2.12.1 Safety Population

The Safety Population will include all randomized NHVs who received at least 1 dose of BT200/placebo. Subjects will be analyzed according to the treatment that they actually received. The Safety Population will be used for all safety endpoints.

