5.3 Biomarker

The following tables will be performed for VWF antigen [%], VWF propeptide [mIU/mL], Factor VIIIc activity [%], aPTT FS [sec], Thrombin generation CAT assay (Thrombinoscope) [nM], Fibrin D-dimer [mIU/mL] and Prothrombin fragment F1.2 [mIU/mL]. Corresponding details on the subject level will be provided in data listings:

- Absolute values by time point
- Absolute change from randomization by time point
- Relative change [%] from randomization by time point

The following figures will be provided for VWF antigen [%], VWF propeptide [mIU/mL], Factor VIIIc activity [%], aPTT FS [sec], Thrombin generation CAT assay (Thrombinoscope) [nM] and Fibrin D-dimer [mIU/mL] and Prothrombin fragment F1.2 [mIU/mL] separately:

- Absolute values by subject: For every subject separately, the time course over of the parameters mentioned above will be drawn, where the actual measurement time point will be shown on x-axis (hours) and the parameters values will be drawn on the y-axis.
- Absolute values by cohort: One graph will be drawn that includes the data of all cohorts. One line will be drawn per cohort, where the x-axis will show the planned time point of measurement (in hours) and the y-axis will show the mean value of the respective cohort incl. standard error. Measurements of all scheduled visits will be included, where the EOS visit will be treated as the last visit.

Details are specified in Section 7.

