6.3 Laboratory Parameters

Laboratory data from scheduled visits and early termination visits will be tabulated. Listings will additionally include results from unscheduled visits.

The following parameters will be assessed in the study and will be included in the statistical analysis:

- Hematology
 - Hemoglobin
 - Hematocrit
 - Red blood cells
 - White blood cells
 - Lymphocytes
 - Monocytes
 - Neutrophils
 - Eosinophils
 - Basophils
 - Platelets
 - Reticulocytes
- Coagulation
 - Prothrombin time
- Clinical Chemistry
 - Sodium
 - Potassium
 - Calcium
 - Chloride
 - Aspartate aminotransferase
 - Alanine aminotransferase
 - Alkaline phosphatase
 - Lactate dehydrogenase
 - Gamma-glutamyltransferase
 - Bilirubin
 - C-reactive protein
 - Blood Urea Nitrogen
 - Creatinine

- Glucose
- Urinalysis
 - Specific gravity
 - pH
 - Leukocytes
 - Nitrite
 - Protein
 - Glucose
 - Ketones
 - Urobilinogen
 - Bilirubin
 - Erythrocytes

Quantitative laboratory parameters (i.e., hematology, clinical chemistry, coagulation, pH, Specific Gravity) will be analyzed descriptively:

- Absolute values by parameter and time point (summary statistics)
- Absolute change from randomization by parameter and time point (summary statistics)
- Relative change from randomization by parameter and time point (summary statistics)
- Number of subjects with values above/below normal range by parameter and time point (frequency statistics)

Qualitative urinalysis parameters will be analyzed by tabulation of urinalysis result by parameter and time point (frequency statistics)

One set of data listings will show parameters outside normal range (hematology, coagulation, clinical chemistry, quantitative urinalysis parameters) and abnormal qualitative urinalysis values, respectively.

For every parameter, boxplots showing the absolute values by study day will be provided.

All parameters will be analyzed using the unit registered by study site in the eCRF. No unit conversion will be done.

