14.x.2.1.4	Yes	PFA-100 [sec]: Absolute values by time point (PP Population)	
14.x.2.1.5	No	PFA-100 [sec]: Absolute change from randomization by time point (PP Population)	
14.x.2.1.6	No	PFA-100 [sec]: Relative change [%] from randomization by time point (PP Population)	
14.x.2.1.7	Yes	REAADS: Absolute values by time point (PP Population)	
14.x.2.1.8	No	REAADS: Absolute change from randomization by time point (PP Population)	
14.x.2.1.9	No	REAADS: Relative change [%] from randomization by time point (PP Population)	
14.x.2.1.10	Yes	VWF:RiCo [%]: Absolute values by time point (PP Population)	
14.x.2.1.11	No	VWF:RiCo [%]: Absolute change from randomization by time point (PP Population)	
14.x.2.1.12	No	VWF:RiCo [%]: Relative change [%] from randomization by time point (PP Population)	
14.x.2.1.13	Yes	VWF antigen [%]: Absolute values by time point (PP Population)	
14.x.2.1.14	No	VWF antigen [%]: Absolute change from randomization by time point (PP Population)	
14.x.2.1.15	No	VWF antigen [%]: Relative change [%] from randomization by time point (PP Population)	
14.x.2.1.16	Yes	VWF propeptide [mIU/mL]: Absolute values by time point (PP Population)	
14.x.2.1.17	No	VWF propeptide [mIU/mL]: Absolute change from randomization by time point (PP Population)	
14.x.2.1.18	No	VWF propeptide [mIU/mL]: Relative change [%] from randomization by time point (PP Population)	
14.x.2.1.19	Yes	Factor VIIIc activity [%]: Absolute values by time point (PP Population)	
14.x.2.1.20	No	Factor VIIIc activity [%]: Absolute change from randomization by time point (PP Population)	
14.x.2.1.21	No	Factor VIIIc activity [%]: Relative change [%] from randomization by time point (PP Population)	
14.x.2.1.22	Yes	aPTT FS [sec]: Absolute values by time point (PP Population)	
14.x.2.1.23	No	aPTT FS [sec]: Absolute change from randomization by time point (PP Population)	
14.x.2.1.24	No	aPTT FS [sec]: Relative change from randomization by time point (PP Population)	
14.x.2.1.25	Yes	Thrombin generation CAT assay [nM]: Absolute values by time point (PP Population)	

14.x.2.1.26	No	Thrombin generation CAT assay [nM]: Absolute change from randomization by time point (PP Population)	
14.x.2.1.27	No	Thrombin generation CAT assay [nM]: Relative change [%] from randomization by time point (PP Population)	
14.x.2.1.28	Yes	Fibrin D-dimer [mIU/mL]: Absolute values by time point (PP Population)	
14.x.2.1.29	No	Fibrin D-dimer [mIU/mL]: Absolute change from randomization by time point (PP Population)	

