14.x.2.1.30	No	Fibrin D-dimer [mIU/mL]: Relative change [%] from randomization by time point (PP Population)	
14.x.2.1.31	Yes	Prothrombin fragment F1.2 [mIU/mL]: Absolute values by time point (PP Population)	
14.x.2.1.32	No	Prothrombin fragment F1.2 [mIU/mL]: Absolute change from randomization by time point (PP Population)	
14.x.2.1.33	No	Prothrombin fragment F1.2 [mIU/mL]: Relative change [%] from randomization by time point (PP Population)	
14.x.2.1.34	No	ADA results by time point (PP Population)	
14.x.2.2.1-14.x.2.2.34	No	Repeat tables 14.x.2.1.1-14.x.2.1.34 for Safety Population	
Safety Analysis			
AEs and Bleeding Events			
14.x.3.1.1	Yes	AE and bleeding event overview (Safety Population)	
 Any AE or bleeding event Any related AE or bleeding event Any severe AE or bleeding event Any related severe AE or bleeding event Any serious AE or bleeding event Any related serious AE or bleeding event Any Hemorrhage (MedDRA SMQ) Any AEs or bleeding events leading to permanently study drug discontinuation or leading to withdrawn from study Any related AEs or bleeding events leading to permanently study drug discontinuation or leading to withdrawn from study (repeat contents for bleeding events) Any Hemorrhage Event (MedDRA SMQ)

			
 • All embolic and thrombotic events (SMQ) • Embolic and thrombotic events, arterial (SMQ) • Embolic and thrombotic events, vessel type unspecified and mixed arterial and venous (SMQ) • Embolic and thrombotic events, venous (SMQ) 
Incl. 2-sided 95% CIs

14.x.3.1.2	Yes	AEs and bleeding events overall and by SOC and PT (Safety Population)	
14.x.3.1.3	Yes	Related AEs and bleeding events overall and by SOC and PT (Safety Population)	
14.x.3.1.4	Yes	Severe AEs and bleeding events overall and by SOC and PT (Safety Population)	
14.x.3.1.5	Yes	Related severe AEs and bleeding events overall and by SOC and PT (Safety Population)	
14.x.3.1.6	Yes	Serious AEs and bleeding events overall and by SOC and PT (Safety Population)	
14.x.3.1.7	Yes	Related serious AEs and bleeding events overall and by SOC and PT (Safety Population)	
14.x.3.1.8	Yes	AEs and bleeding events by maximum severity (Safety Population)	Incl. 2-sided 95% CIs
14.x.3.1.9	Yes	Related AEs and bleeding events by maximum severity (Safety Population)	Incl. 2-sided 95% CIs
14.x.3.1.10	Yes	Serious AEs and bleeding events by maximum severity (Safety Population)	Incl. 2-sided 95% CIs

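### Only prothrombin time is counted against normal limits in the safety coagulation analysis; aPTT, Factor VIIIc, D-dimer and F1.2 get no out-of-range count

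*SAP*

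**What the plan says.** SAP Section 6.3 opens its list of safety laboratory tests with "The following parameters will be assessed in the study and will be included in the statistical analysis". Under Coagulation the only entry is "Prothrombin time". Quantitative tests on that list get values, changes, and a count of subjects above or below the normal range. Listing 16.2.x.3.17 adds the laboratory's limits and a clinical-relevance field.

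The other coagulation-type tests are in SAP Section 5.3, which names "Factor VIIIc activity [%], aPTT FS [sec], Thrombin generation CAT assay (Thrombinoscope) [nM], Fibrin D-dimer [mIU/mL] and Prothrombin fragment F1.2 [mIU/mL" after VWF antigen and propeptide. For these the plan is absolute values, absolute change and relative change. The topline table for aPTT, for example, is "aPTT FS [sec]: Absolute values by time point (PP Population"). A single row, flagged No for the topline, adds "Repeat tables 14.x.2.1.1-14.x.2.1.34 for Safety Population".

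The primary endpoint (SAP Section 1.3.1, and the protocol synopsis) includes "clinically relevant laboratory abnormalities, vital signs, ECGs, or physical findings suggestive of one or more specific target organs for toxicity of BT200". SAP Section 2.12.1 states: "The Safety Population will be used for all safety endpoints".

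**The concern.** The primary endpoint treats laboratory abnormalities as a component in their own right, joined to drug-related AEs by and/or. For hematology, chemistry and quantitative urinalysis the SAP serves that component with a systematic count of out-of-range values. For coagulation it does so for one test only.

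The trial has reason to look further. BT200 binds VWF. The protocol's summary of changes for Version 1.5.1 reports an unexpected rise in VWF antigen after BT200 treatment. The SAP itself tabulates hemorrhage and embolic/thrombotic SMQs. Yet the coagulation abnormality table and listing could look clean while aPTT, Factor VIIIc or D-dimer lay outside the laboratory's limits in treated subjects. Means and quartiles for a BT200 cohort of six, shown without limits, do not tell the reader how many subjects were abnormal.

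**Working it through.** No formula applies: the study is descriptive and the SAP gives no figure to reproduce. The check follows each test through SAP Sections 5.3, 6.3, 7.1 and 7.2. The Safety Population repeat row maps 14.x.2.1.n to 14.x.2.2.n, which gives the last column for the four biomarkers.

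| Test | SAP section | Out-of-range count | Limits and relevance in a listing | Topline absolute-value table | Absolute-value table in the Safety Population |
|---|---|---|---|---|---|
| Prothrombin time | 6.3 | 14.x.3.1.22 | 16.2.x.3.17 | 14.x.3.1.19 (Safety) | 14.x.3.1.19 |
| Factor VIIIc | 5.3 | none | none | 14.x.2.1.19 (PP) | 14.x.2.2.19 (final only) |
| aPTT FS | 5.3 | none | none | 14.x.2.1.22 (PP) | 14.x.2.2.22 (final only) |
| D-dimer | 5.3 | none | none | 14.x.2.1.28 (PP) | 14.x.2.2.28 (final only) |
| F1.2 | 5.3 | none | none | 14.x.2.1.31 (PP) | 14.x.2.2.31 (final only) |

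1. Out-of-range count: 1 of 5 tests. For the four biomarkers, 0 of 4.
2. Limits or clinical-relevance field in a listing: 0 of 4. Both biomarker listings (each numbered 16.2.x.2.2) carry the result and its changes, but no limits and no relevance field.
3. Topline summary table in the Safety Population: 0 of 4. In the final analysis: 4 of 4.
4. Topline reach: SAP Section 2.2 plans a topline analysis for Parts A and D only. The biomarker listings are flagged Yes for the topline, and under SAP Section 2.13 listings cover all subjects in the database. The results of a subject excluded from the PP Population are therefore visible at topline, though not in a summary table.
5. Route into the primary safety tables: AEs are tabulated in the Safety Population at topline, and the hemorrhage SMQ in SAP Section 6.2.2 includes a laboratory sub-query. An abnormal value enters there if the investigator reports it as an AE. No other planned table counts it.

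Section 5.3 lists seven assays in all. VWF antigen, VWF propeptide and thrombin generation also have no limits. Leaving them out of the count (7 − 3 = 4) is a judgement about which tests most resemble a safety panel.

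**The case against.** The best defence is that the SAP follows the protocol. The synopsis lists "aPTT FS (elagic acid") and Factor VIIIc as exploratory biomarkers, and for a drug acting on VWF they can be read as measures of pharmacology. That stands: this is a choice of analysis, not a contradiction between documents. But a test can serve both purposes. D-dimer and F1.2 are in neither document's endpoint list, so the same defence does not cover them.

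A reader might infer that abnormalities in these tests can never enter the primary endpoint tables. The documents do not support that. The AE route is open, the hemorrhage SMQ includes laboratory terms, and clinically evident bleeding has its own tables (14.x.3.1.14 to .18). What is missing is a systematic count that does not depend on investigator reporting.

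A reader might also infer that subjects outside the PP Population are lost from these analyses. They are not. SAP Section 5 requires both populations, the repeat row supplies the final tables, and the topline listings include everyone. None of this supplies a normal range, so the main gap remains in the final analysis.

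Finally, it is tempting to argue that prothrombin time is the test least able to respond to BT200. Neither document says so, nor do they tie D-dimer or F1.2 to the drug's target. The point does not need either claim.

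**Conclusion.** The gap is real but minor. Of five coagulation-type tests, only prothrombin time is set against normal limits. The other four have values and changes but no out-of-range count, no limits and no relevance field at any stage, although the primary endpoint includes clinically relevant laboratory abnormalities. The PP restriction is a smaller matter, confined for the tables to the Part A and D topline summaries. Its effect cannot be sized, because the documents give no PP exclusion rate.

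The conclusion rests on the SAP's own lists of parameters, tables and listings. The protocol's laboratory sampling appendices were not available for this check. It is therefore an assumption that the laboratory can supply reference limits for these assays, and unknown whether the investigator's judgement of clinical relevance is captured for them.

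**What to change.** Keep the biomarker classification and all Section 5.3 tables. Then:

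- Add aPTT, Factor VIIIc and D-dimer, and F1.2 if the laboratory has a reference range, to Table 14.x.3.1.22 and Listing 16.2.x.3.17 in the Safety Population. Show the laboratory's limits, and the clinical-relevance field where it is captured.
- Set the topline flag to Yes for the Safety Population absolute-value tables 14.x.2.2.19, .22, .28 and .31.
- State in Section 6.3 that these tests are counted there as well as being summarised under 5.3.

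There is no need to add them to Tables 14.x.3.1.19 to .21, because the 14.x.2.2 series already gives values and changes in the Safety Population.

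The cost is obtaining reference ranges and minor programming; no new samples are needed. Some out-of-range counts may reflect expected pharmacology rather than toxicity, and a footnote should say so.

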6.4 Other Safety Parameters

Other safety data from scheduled visits will be tabulated as described below. Listings will additionally include results from unscheduled visits or early termination visit.

Results from vital signs (systolic blood pressure [mmHg], diastolic blood pressure [mmHg], heart rate [beats/min], body temperature [C] and body weight [kg]) and ECG will be tabulated descriptively by:

- Absolute values by parameter and time points (summary statistics)
- Absolute changes from randomization by parameter and time points (summary statistics)
- Number of subjects with clinically relevant vital signs results by parameter and time point (frequency statistics)

- ECG Interpretation (normal/abnormal/abnormal, clinically relevant/abnormal, not clinically relevant) by time point (frequency statistics)
- Physical examination results (normal/abnormal) by body system and time point (frequency statistics)

Absolute values of vital signs parameters and continuous ECG parameters will be provided by time point. The x-axis will show the study day. A separate figure will be provided for every parameter.

Details are specified in Section [7](#).

7. LIST OF TABLES, DATA LISTINGS AND FIGURES

The x in the numbering of the TLFs below has to be replaced by 1 for Part A, 2 for Part B, 3 for Part C and 4 for Part D.

7.1 List of Tables

No	Topline Analysis	Title	Content/Comment
Overall Study Information and Baseline Evaluation			
14.x.1.1.1	Yes	Patient Overview	
 • Number of subjects in Safety Population • Number of subjects in PP Population • Number of sentinel subjects (only applicable for Part A) • Number of randomized subjects • Screening of coronavirus (only applicable for Part B and C) 
Columns: Not randomized, column for each BT200 dose level and Placebo

14.x.1.1.2	No	Number of Screening Failures and Reasons	One column for all subjects
14.x.1.1.3	No	Subjects by Visit (Safety Population)	
14.x.1.1.4	No	End of Study Information (Safety Population)	
 • Visit attendance status • Primary reason for early termination • Early terminations due to Covid-19
14.x.1.1.5	No	Protocol Deviations (Safety Population)	
 • Any major protocol deviation • Major protocol deviations by category • Any minor protocol deviation • Minor protocol deviations by category
14.x.1.1.6	Yes	Demographic Information (Safety Population)	
 • Gender • Age [years] • Race • Ethnicity • Body height [cm] • Body weight [kg] • BMI [kg/m²] at screening
14.x.1.1.7	No	Medical History Overall and by SOC and PT (Safety Population)	
 • Any medical history • By SOC and PT
14.x.1.1.8	No	Prior Medications Overall and by ATC Level (Safety Population)	
 • Any prior medication • By ATC level
14.x.1.1.9	No	Concomitant Medications Overall and by ATC Level (Safety Population)	
 • Any concomitant medication • By ATC level
14.x.1.1.10	No	Prior Procedures Overall and by SOC and PT (Safety Population)	
 • Any prior procedures • By SOC and PT
14.x.1.1.11	No	Concomitant Procedures Overall and by SOC and PT (Safety Population)	
 • Any concomitant procedures • By SOC and PT

14.x.1.2.3- 14.x.1.2.5	No	Repeat tables 14.x.1.1.3-5 for PP Population	
Pharmacodynamics/Biomarker/Immunogenicity			
14.x.2.1.1	Yes	Multiplate Aggregometer [U]: Absolute values by time point (PP Population)	
14.x.2.1.2	No	Multiplate Aggregometer [U]: Absolute change from randomization by time point (PP Population)	
14.x.2.1.3	No	Multiplate Aggregometer [U]: Relative change [%] from randomization by time point (PP Population)	
14.x.2.1.4	Yes	PFA-100 [sec]: Absolute values by time point (PP Population)	
14.x.2.1.5	No	PFA-100 [sec]: Absolute change from randomization by time point (PP Population)	
14.x.2.1.6	No	PFA-100 [sec]: Relative change [%] from randomization by time point (PP Population)	
14.x.2.1.7	Yes	REAADS: Absolute values by time point (PP Population)	
14.x.2.1.8	No	REAADS: Absolute change from randomization by time point (PP Population)	
14.x.2.1.9	No	REAADS: Relative change [%] from randomization by time point (PP Population)	
14.x.2.1.10	Yes	VWF:RiCo [%]: Absolute values by time point (PP Population)	
14.x.2.1.11	No	VWF:RiCo [%]: Absolute change from randomization by time point (PP Population)	
14.x.2.1.12	No	VWF:RiCo [%]: Relative change [%] from randomization by time point (PP Population)	
14.x.2.1.13	Yes	VWF antigen [%]: Absolute values by time point (PP Population)	
14.x.2.1.14	No	VWF antigen [%]: Absolute change from randomization by time point (PP Population)	
14.x.2.1.15	No	VWF antigen [%]: Relative change [%] from randomization by time point (PP Population)	
14.x.2.1.16	Yes	VWF propeptide [mIU/mL]: Absolute values by time point (PP Population)	
14.x.2.1.17	No	VWF propeptide [mIU/mL]: Absolute change from randomization by time point (PP Population)	
14.x.2.1.18	No	VWF propeptide [mIU/mL]: Relative change [%] from randomization by time point (PP Population)	
14.x.2.1.19	Yes	Factor VIIIc activity [%]: Absolute values by time point (PP Population)	
14.x.2.1.20	No	Factor VIIIc activity [%]: Absolute change from randomization by time point (PP Population)	
14.x.2.1.21	No	Factor VIIIc activity [%]: Relative change [%] from randomization by time point (PP Population)	
14.x.2.1.22	Yes	aPTT FS [sec]: Absolute values by time point (PP Population)	
14.x.2.1.23	No	aPTT FS [sec]: Absolute change from randomization by time point (PP Population)	
14.x.2.1.24	No	aPTT FS [sec]: Relative change from randomization by time point (PP Population)	
14.x.2.1.25	Yes	Thrombin generation CAT assay [nM]: Absolute values by time point (PP Population)	

14.x.2.1.26	No	Thrombin generation CAT assay [nM]: Absolute change from randomization by time point (PP Population)	
14.x.2.1.27	No	Thrombin generation CAT assay [nM]: Relative change [%] from randomization by time point (PP Population)	
14.x.2.1.28	Yes	Fibrin D-dimer [mIU/mL]: Absolute values by time point (PP Population)	
14.x.2.1.29	No	Fibrin D-dimer [mIU/mL]: Absolute change from randomization by time point (PP Population)	
14.x.2.1.30	No	Fibrin D-dimer [mIU/mL]: Relative change [%] from randomization by time point (PP Population)	
14.x.2.1.31	Yes	Prothrombin fragment F1.2 [mIU/mL]: Absolute values by time point (PP Population)	
14.x.2.1.32	No	Prothrombin fragment F1.2 [mIU/mL]: Absolute change from randomization by time point (PP Population)	
14.x.2.1.33	No	Prothrombin fragment F1.2 [mIU/mL]: Relative change [%] from randomization by time point (PP Population)	
14.x.2.1.34	No	ADA results by time point (PP Population)	
14.x.2.2.1-14.x.2.2.34	No	Repeat tables 14.x.2.1.1-14.x.2.1.34 for Safety Population	
Safety Analysis			
AEs and Bleeding Events			
14.x.3.1.1	Yes	AE and bleeding event overview (Safety Population)	
 Any AE or bleeding event Any related AE or bleeding event Any severe AE or bleeding event Any related severe AE or bleeding event Any serious AE or bleeding event Any related serious AE or bleeding event Any Hemorrhage (MedDRA SMQ) Any AEs or bleeding events leading to permanently study drug discontinuation or leading to withdrawn from study Any related AEs or bleeding events leading to permanently study drug discontinuation or leading to withdrawn from study (repeat contents for bleeding events) Any Hemorrhage Event (MedDRA SMQ)

			
 • All embolic and thrombotic events (SMQ) • Embolic and thrombotic events, arterial (SMQ) • Embolic and thrombotic events, vessel type unspecified and mixed arterial and venous (SMQ) • Embolic and thrombotic events, venous (SMQ) 
Incl. 2-sided 95% CIs

14.x.3.1.2	Yes	AEs and bleeding events overall and by SOC and PT (Safety Population)	
14.x.3.1.3	Yes	Related AEs and bleeding events overall and by SOC and PT (Safety Population)	
14.x.3.1.4	Yes	Severe AEs and bleeding events overall and by SOC and PT (Safety Population)	
14.x.3.1.5	Yes	Related severe AEs and bleeding events overall and by SOC and PT (Safety Population)	
14.x.3.1.6	Yes	Serious AEs and bleeding events overall and by SOC and PT (Safety Population)	
14.x.3.1.7	Yes	Related serious AEs and bleeding events overall and by SOC and PT (Safety Population)	
14.x.3.1.8	Yes	AEs and bleeding events by maximum severity (Safety Population)	Incl. 2-sided 95% CIs
14.x.3.1.9	Yes	Related AEs and bleeding events by maximum severity (Safety Population)	Incl. 2-sided 95% CIs
14.x.3.1.10	Yes	Serious AEs and bleeding events by maximum severity (Safety Population)	Incl. 2-sided 95% CIs
14.x.3.1.11	Yes	Related serious AEs and bleeding events by maximum severity (Safety Population)	Incl. 2-sided 95% CIs
14.x.3.1.12	Yes	AEs and bleeding events leading to permanently study drug discontinuation or leading to withdrawn from study by SOC and PT (Safety Population)	
14.x.3.1.13	Yes	Related AEs and bleeding events leading to permanently study drug discontinuation or leading to withdrawn from study by SOC and PT (Safety Population)	
14.x.3.1.14	Yes	Bleeding Events by SOC and PT (Safety population)	Incl. 2-sided 95% CI
14.x.3.1.15	Yes	Major bleeding events overall and by SOC and PT (Safety Population)	
14.x.3.1.16	Yes	Total ISTH Bleeding Score (Safety Population)	
14.x.3.1.17	Yes	Bleeding Assessment Score by Symptom (Safety Population)	
14.x.3.1.18	Yes	Maximum Bleeding Assessment Score (Safety Population)	
Laboratory parameter			
14.x.3.1.19	Yes	Hematology and Coagulation: Absolute values by time point (Safety Population)	
14.x.3.1.20	Yes	Hematology and Coagulation: Absolute change from randomization by time point (Safety Population)	
14.x.3.1.21	Yes	Hematology and Coagulation: Relative change from randomization by time point (Safety Population)	

14.x.3.1.22	Yes	Hematology and Coagulation: Subjects outside normal range by time point (Safety Population)	
14.x.3.1.23	Yes	Clinical Chemistry: Absolute values by time point (Safety Population)	
14.x.3.1.24	Yes	Clinical Chemistry: Absolute change from randomization by time point (Safety Population)	
14.x.3.1.25	Yes	Clinical Chemistry: Relative change from randomization by time point (Safety Population)	
14.x.3.1.26	Yes	Clinical Chemistry: Subjects outside normal range by time point (Safety Population)	
14.x.3.1.27	Yes	Quantitative Urinalysis: Absolute values by time point (Safety Population)	
14.x.3.1.28	Yes	Quantitative Urinalysis: Absolute change from randomization by time point (Safety Population)	
14.x.3.1.29	Yes	Quantitative Urinalysis: Relative change from randomization by time point (Safety Population)	
14.x.3.1.30	Yes	Quantitative Urinalysis: Subjects outside normal range by time point (Safety Population)	
14.x.3.1.31	Yes	Qualitative Urinalysis by time point (Safety Population)	
14.x.3.1.32	Yes	Vital Signs: Absolute values by time point (Safety Population)	
 • systolic blood pressure [mmHg] • diastolic blood pressure [mmHg] • heart rate [beats/min] • body temperature [C] • body weight [kg]
14.x.3.1.33	Yes	Vital Signs: Absolute change from randomization by time point (Safety Population)	Content see Table 14.x.3.1.32
14.x.3.1.34	Yes	Subjects with clinically relevant vital signs by time point (Safety Population)	Content see Table 14.x.3.1.32
14.x.3.1.35	Yes	ECG: Absolute values by time point (Safety Population)	
 • PQ [ms] • QRS [ms] • QT [ms] • QTcF [ms] • P [ms] • RR [ms] • PP [ms] • P [degree] • QRS [degree] • T [degree]
14.x.3.1.36	Yes	ECG: Absolute change from randomization by time point (Safety Population)	Content see Table 14.x.3.1.35
14.x.3.1.37	Yes	Subjects with clinically relevant ECG values by time point (Safety Population)	Content see Table 14.x.3.1.35
14.x.3.1.38	Yes	ECG Interpretation by time point (Safety Population)	
 • normal • abnormal • abnormal, clinically relevant • abnormal, not clinically relevant
14.x.3.1.39	Yes	Physical Examination results by body system and time point (Safety Population)	
 • normal • abnormal

